13.2.3.4 Lipid Profile

During the Phase 2b double-blind study of ataluren in nmDMD (PTC124-GD-007-DMD), mean total cholesterol and triglycerides were in the upper range of normal at baseline and increased on study, reaching borderline high or high values. Although the values tended to stabilize early in the trial and did not increase further with continued use of ataluren, monitoring the changes in patients' lipid profile is warranted. For this reason, total cholesterol, LDL, HDL, and triglycerides will be evaluated at each visit to monitor for changes in lipid profile values.

13.2.3.5 Blood Pressure Assessment

During the Phase 2b double-blind study of ataluren in nmDMD (PTC124-GD-007-DMD), 6 patients – all receiving corticosteroids – had hypertension (or increased blood pressure) reported as adverse events (0 for ataluren 20, 20, 40 mg/kg, 5 for ataluren 10, 10, 20 mg/kg, and 1 for placebo). For this reason, blood pressure will be monitored via standardized procedures at each visit.

13.2.3.6 Other Non-Clinical Findings

Single lipomatous, non metastatic tumors, determined to be malignant hibernomas originating in brown adipose tissue were identified in 6 rats during a 26 week toxicity study. In a second 26 week rat study, no malignant hibernomas were observed in any dose group, including the high dose group (1200 mg/kg/day). The exact correlative relevance of this finding is unclear given the lack of reproducibility in rats, the different physiology of brown fat in rats relative to humans [Cannon 2004, Iatropoulos 2004], the very young age of the rats used in these studies, the lack of ataluren genotoxicity, and the extreme rarity and generally benign course of hibernomas in humans [Furlong 2001].

Urinary bladder tumors were observed in 3/60 females at the high dose of 300 mg/kg/day in the 24-month carcinogenicity study in rats. This dose exceeded the maximum tolerated dose (MTD), based on an average 23% reduction in body weight gain in comparison to vehicle controls throughout the study. In addition, the proposed mode of urinary bladder tumor formation (presence of calculi) in rats is not considered relevant to humans. Mean steady state exposures in female rats at the mid-dose of 100 mg/kg/day and in male rats at the high-dose of 300 mg/kg/day were 4 and 6 times, respectively, the steady state exposure in patients administered ataluren at the morning, midday and evening doses of 10, 10 and 20 mg/kg/day, respectively.

Long-term post-treatment follow-up safety data currently available from the patients dosed with ataluren to date in the clinical studies, some for over 7 years, indicate no increased risk of tumors.

13.2.4 Other Abnormalities

Recommendations for interruption of dosing are provided in Section 6.3.1, with the general intent that a Grade 4 (life-threatening) event should result in immediate cessation of dosing while awaiting confirmation of the abnormal laboratory value, a Grade 3 (severe) event may require confirmation of the abnormal laboratory value before cessation of dosing, and a Grade 2 (moderate) event may prompt further evaluation while ataluren dosing continues. It is intended that these recommendations be viewed flexibly, the type and context for any adverse event or laboratory abnormality must be considered in taking action.

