Table 3 below provides information on actions to be taken in the event that abnormalities are noted in specified laboratory parameters. Thresholds are provided for interrupting ataluren immediately, for interrupting ataluren after confirmation of a value beyond the threshold, or for continuing ataluren while evaluating for potential drug-related toxicity. For adverse events or laboratory abnormalities not listed in Table 3 below, the investigator should use his/her judgment in determining whether the event or abnormality is clinically significant, whether diagnostic evaluation is warranted, and whether potential interruption of ataluren therapy is appropriate.

Table 3. Safety Monitoring Parameters and Actions To Be Taken

Organ System and Laboratory Parameter	Stop Study Drug Immediately, Confirm Abnormal Value, and Then Start Work-Up	Stop Study Drug After Confirming ^a Abnormal Value, and Then Start Work-Up	Continue Study Drug, Confirm Abnormal Value, and then Start Work-Up ^a
Hepatic			
Serum total bilirubin	≥Grade 3 (≥3.0 x ULN)	Grade 2 (1.5 – 3.0 x ULN)	
Serum GGT	≥Grade 3 (≥5.0 x ULN)	Grade 2 (>2.5 – 5.0 x ULN)	
Serum ALT			↑ of > 150 U/L with stable or ↓ CK
Adrenal			
Plasma ACTH		>ULN (and plasma cortisol <lln)< td="">>ULN (and cortisol WNL)	</lln)<>	>ULN (and cortisol WNL)
Renal			
Serum cystatin C	>2.00 mg/L	>1.33 – 2.00 mg/L	
Serum creatinine	≥ Grade 2 (≥1.5 x ULN for age)	Grade 1 (>ULN – 1.5 x ULN for age)	
Serum BUN	≥3.0 x ULN	≥1.5 – 3.0 x ULN	
Urine protein: urine creatinine (spot)		>0.40 mg:mg	
Urine protein: urine osmolality (spot)		>0.30 mg/L:mOsm/kg	
Urine blood (by dipstick)	4+ (Large)	3+ (Moderate)	2+ (Small)
Serum electrolytes	Grade 3-4	Grade 2	Grade 1
Serum Na+, high	>155 mmol/L	>150 – 155 mmol/L	
Serum Na+, low	<130 mmol/L		
Serum K+, high	>6.0 mmol/L	>5.5 – 6.0 mmol/L	
Serum K+, low	<3.0 mmol/L		
Serum Mg ²⁺ , high	>1.23 mmol/L		
Serum Mg ²⁺ , low	<0.4 mmol/L	<0.5 – 0.4 mmol/L	
Total serum Ca ²⁺ , high	>3.1 mmol/L	>2.9 – 3.1 mmol/L	
Total serum Ca ²⁺ , low	<1.75 mmol/L	<2.0 – 1.75 mmol/L	
Serum phosphorous	<0.6 mmol/L	<0.8 – 0.6 mmol/L	
Serum HCO ₃ -	<11 mmol/L	<16 – 11 mmol/L	

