a Laboratory abnormalities may be confirmed immediately or at the next scheduled clinic visit based on investigator judgment. **Abbreviations:** ACTH = adrenocorticotropic hormone, ALT = alanine aminotransferase, BUN = blood urea nitrogen, Ca²⁺ = calcium, CK = creatine kinase, GGT = gamma glutamyl transferase, HCO₃₋ = bicarbonate, K+ = potassium, Mg²⁺ = magnesium, Na+ = sodium, ULN = upper limit of normal, WNL = within normal limits

It should be noted that blood samples for renin and aldosterone determinations will also be obtained at screening, and, as necessary, for patients with treatment-emergent evidence of adrenal dysfunction. Changes in these laboratory parameters alone will not be exclusionary or reason for study drug discontinuation because renin and aldosterone values are markedly affected by age and normal reference ranges are too narrow to reliably use as guidance for treatment discontinuation in this study population. In addition, renin and aldosterone values may be affected by angiotensin-converting enzyme (ACE) inhibitors, and angiotensin-receptor blockers (ARBs). Changes in renin and aldosterone will be viewed in context with other laboratory findings.

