13.2.3.1.2. Hepatic Monitoring Plan

Muscle breakdown results in ALT and AST values that are commonly 10- to 20-fold > ULN (Grade 3-4) in patients with DBMD. Consequently, it is not practical to exclude patients with high serum AST or ALT concentrations from enrollment in this study, and monitoring for hepatotoxicity must rely primarily on following patients for increases in bilirubin or GGT. Consistent with well-established guidelines [Abboud 2007] applied in this disease setting, even modest (Grade 2) alteration in bilirubin or GGT values should prompt interruption of ataluren. While serum ALT or AST values cannot routinely serve as measures of hepatic injury in boys with DBMD, significant increases in ALT (>150 U/L) in conjunction with a stable or falling CK should prompt increased frequency of laboratory monitoring and possibly an evaluation for potential hepatotoxicity.

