- Urine Blood: Blood in the urine may indicate pathology of the renal parenchyma or of the urinary collecting system (eg, ureters, bladder, and urethra). Like proteinuria, hematuria is commonly found in patients with minimal changes in GFR due to renal (particularly glomerular) dysfunction [National Kidney Foundation 2002]. Confirmed, persistent evidence of urinary blood by dipstick and/or microscopic examination will prompt further evaluation. Ultrasound or other imaging can evaluate for a potential renal cause for bleeding. Urology consultation can be obtained to assess for post-renal sources of hematuria. Clotting function and use of drugs that may impair platelet function will be reviewed. Confirmed, persistent hematuria in the absence of a post-renal source of bleeding or a bleeding diathesis will prompt potential interruption/modification of ataluren dosing.
- Serum Electrolytes: Assessments of serum electrolytes (sodium, chloride, potassium, bicarbonate, magnesium, calcium, and phosphorus) provide information regarding renal function that may supplement more primary assessments. Derangements in serum concentrations may reflect altered tubular handling of these ions. With worsening renal function, hyperphosphatemia and hypocalcemia may develop and reductions in serum bicarbonate or elevations in potassium may suggest an impaired ability of proximal tubules or collecting ducts to maintain acid-base balance [National Kidney Foundation 2002].

Given the cardiovascular and neurological consequences of severe derangements of serum potassium, calcium, or magnesium, evaluation of these ions is important to avoid potential secondary complications. Because transient Grade 1 alterations in the concentrations of electrolytes are very unlikely to be associated with significant secondary side effects, alterations to ≥Grade 2 are considered appropriate to prompt potential interruption/modification of ataluren dosing.

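### Protocol 13.2.4 summarises the dose-interruption scheme of Section 6.3.1 with grades that do not match Table 3: one grade more lenient for bilirubin, GGT and electrolytes, two for creatinine

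*Protocol*

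**What the plan says.** Protocol 13.2.4 (Other Abnormalities) presents itself as a summary of another section: "Recommendations for interruption of dosing are provided in Section 6.3.1, with the general intent". It then gives three steps:

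- At Grade 4, drug stops straight away and the laboratory result is checked afterwards.
- At Grade 3, stopping may wait until the result has been checked.
- At Grade 2, drug goes on: "and a Grade 2 (moderate) event may prompt further evaluation while ataluren dosing continues".

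It closes by asking that the recommendations be applied flexibly and in context.

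Section 6.3.1 introduces Table 3 in these terms: "Thresholds are provided for interrupting ataluren immediately, for interrupting ataluren after confirmation of a value beyond the threshold", with a third column for continuing drug during evaluation. Table 3 assigns CTCAE grades to these columns for bilirubin, GGT, creatinine and serum electrolytes. For anything not in Table 3, 6.3.1 leaves the decision to the investigator.

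Two other rationale passages deal with Grade 2. Protocol 13.2.3.1.2 says "even modest (Grade 2) alteration in bilirubin or GGT values should prompt interruption of ataluren". The electrolyte paragraph of 13.2.3.3.2 says, more softly, "alterations to ≥Grade 2 are considered appropriate to prompt potential interruption/modification of ataluren dosing". The creatinine paragraph of 13.2.3.3.2 treats a value above the age-specific normal range as a reason to re-evaluate and possibly interrupt or modify dosing.

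**The concern.** Table 3 is the trial's operative safety rule for its target organs. A rationale section that restates the rule with shifted grades gives an investigator or medical monitor a second, conflicting statement of what the protocol intends. For a confirmed Grade 2 bilirubin, GGT or electrolyte value, one text leads to stopping and the other to continued dosing.

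Safety is the primary endpoint. Protocol 13.2.5 says the recommendations are meant to produce a medically appropriate and consistent response across investigators. A protocol that states the grade scheme in two ways works against that aim.

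**Working it through.** There is no figure to reproduce. The check sets the two mappings side by side.

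| Action | 13.2.4 | Table 3: bilirubin, GGT | Table 3: electrolytes (header row) | Table 3: creatinine |
|---|---|---|---|---|
| Stop at once, then confirm | Grade 4 | Grade 3 and above | Grade 3-4 | Grade 2 and above |
| Confirm, then stop | Grade 3 (worded as a possibility) | Grade 2 | Grade 2 | Grade 1 |
| Continue while evaluating | Grade 2 | no entry | Grade 1 | no entry |

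**Size of the shift** (grade in 13.2.4 minus grade in Table 3):

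- Lowest grade for an immediate stop: 4 − 3 = 1 for bilirubin, GGT and electrolytes; 4 − 2 = 2 for creatinine.
- Lowest grade for stopping after confirmation: 3 − 2 = 1 for bilirubin, GGT and electrolytes; 3 − 1 = 2 for creatinine.
- Highest grade at which dosing continues: 2 − 1 = 1 for electrolytes, the only graded group with an entry in that column.

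**What this means grade by grade:**

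- Grade 4: the texts agree.
- Grade 3: Table 3 stops at once for all four groups. 13.2.4 may allow confirmation first. Both end in stopping, so the difference is timing.
- Grade 2, bilirubin, GGT and electrolytes: once the value is confirmed, Table 3 stops and 13.2.4 continues. For example, a potassium of 5.8 mmol/L lies in Table 3's range of above 5.5 to 6.0 mmol/L, under stop after confirming. Low sodium, low potassium and high magnesium have no numerical entry in the Grade 2 column, so no range can be quoted for them.
- Grade 2, creatinine: Table 3 stops at once and 13.2.4 continues.
- Grade 1, creatinine: Table 3 stops after confirmation. 13.2.4 does not mention Grade 1.

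**Rows not affected:** cystatin C, BUN, ACTH with cortisol, the two urine protein ratios and urine blood carry no CTCAE grade in Table 3, so a grade-based summary neither matches nor contradicts them.

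**Could 13.2.4 be summarising something else in 6.3.1?** Apart from Table 3, that section contains:

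1. A general paragraph that regards Grade 3 and Grade 4 events as clinically significant, and recurrent or persistent Grade 2 events as sometimes so. It assigns no dosing action to any grade and treats Grades 3 and 4 alike, which 13.2.4 does not.
2. A paragraph on dose-limiting events, which uses no grades.
3. The judgment clause for items outside Table 3, which also uses no grades.

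Table 3 is therefore the only grade-by-grade dosing scheme in 6.3.1 that 13.2.4 could describe.

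**The case against.** The best defence is scope and status. 13.2.4 is headed Other Abnormalities and follows the hepatic, adrenal and renal discussion in 13.2.3, so it may be meant only for parameters outside Table 3. The general paragraph of 6.3.1 gives the cross-reference a possible target there, with a gradient loosely like that of 13.2.4. Section 13 is rationale, sends the reader back to 6.3.1 and asks for flexibility. A site with a potassium of 5.8 mmol/L would be expected to use Table 3.

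Much of this stands. The scope is ambiguous, and no passage tells sites to take dosing actions from 13.2.4. That limits the weight of the point. It does not remove it: on the narrow reading, 13.2.4 attributes to 6.3.1 a grade scheme that 6.3.1 does not contain, and flexibility in applying a rule does not explain two different statements of it. Either reading needs an edit.

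Three stronger inferences are tempting but not supported:

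- **That Grade 3 values lead to opposite actions.** They do not; both texts stop the drug.
- **That following 13.2.4 adds about 84 days of dosing** (12 weeks × 7 days between visits). This relies on Table 3 footnote a: "Laboratory abnormalities may be confirmed immediately or at the next scheduled clinic visit based on investigator judgment". The footnote is marked on the second and third columns of Table 3, not on the immediate-stop column, and 13.2.4 has no such footnote. At Grade 2, Table 3 itself already allows that wait. The documents give no duration attributable to 13.2.4. Nor does the footnote contradict a rule to stop after confirming.
- **That the SAP Table 2 summary depends on which section a site used.** SAP 5.7.2 summarises laboratory abnormalities against fixed thresholds. Classifying a value does not depend on what the site did next.

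**Conclusion.** The inconsistency is real. 13.2.4 is one grade more lenient than Table 3 for bilirubin, GGT and electrolytes, and two grades for creatinine. Its substance is at Grade 2, where the two texts end in different dosing decisions; at Grade 3 the difference is timing only.

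The conclusion assumes that the cross-reference in 13.2.4 means what it says. If 13.2.4 was intended only for parameters outside Table 3, the defect shrinks to an unstated scope and a wrong cross-reference. The weight is minor to moderate, because the operative rule is in 6.3.1 and the conflict lies in rationale text. It also falls if dosing has ended: SAP 5.2 records that the sponsor has decided to discontinue the study. Nothing here says which mapping is clinically right.

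**What to change.** Make one of two wording changes:

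1. Reconcile 13.2.4 with Table 3, 13.2.3.1.2 and the creatinine and electrolyte paragraphs of 13.2.3.3.2, so that a single grade-to-action mapping applies.
2. State in 13.2.4 that it covers only parameters not listed in Table 3, and correct its reference to 6.3.1, which gives no grade-by-grade scheme for those parameters.

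The sponsor's medical team decides which mapping holds. The cost is a wording amendment or a clarification letter to sites, with no new assessments.

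Optionally, SAP 5.7.2 could add a count of how many values crossing each Table 2 threshold were followed by an interruption. Protocol 10.4.3 promises a description of dose modifications, delays and omissions, while SAP 5.6 covers only compliance and treatment duration, so the count would show what sites did. It is one added column and is not needed to resolve the inconsistency.

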13.2.5 Actions to be Taken in Response to Safety Signals

The intent of the recommendations to investigators regarding response to safety signals is to encourage a medically appropriate and consistent approach to adverse events and laboratory abnormalities. While specific monitoring, diagnostic testing, and supportive care measures must be instituted based on the clinical judgment of the investigator, investigators are encouraged to contact the MAPI or PTC Therapeutics medical monitor to obtain guidance and to ascertain whether similar events are being seen at other investigator sites. The availability of advice from hepatology, endocrinology, and nephrology experts retained by PTC Therapeutics is intended to provide a uniformly high level of consultation in support of the investigators and the PTC medical monitor.

The dose interruption and modification provisions are designed to balance a primary concern for patient safety with the potential for observing efficacy in circumstances under which a patient experiencing an adverse event may still be able to continue with dosing at a lower ataluren dose. Interruption of dosing is advocated as the primary response in order to determine reversibility of the adverse finding. Rechallenge permits a patient to proceed with potentially beneficial treatment and enhances understanding of the relatedness of the adverse event to ataluren.

13.2.6 Efficacy Measurements

13.2.6.1 6-Minute Walk Test

Loss of ambulation is one of the most serious complications of DBMD. The 6MWT is an established outcome measure reflecting the global status of all the systems involved in walking, including the neuromuscular, pulmonary, and cardiovascular systems [Takeuchi 2008].

Based on precedent in other neuromuscular disorders [Rubin 2002, Wraith 2004, Muenzer 2006], the 6MWT represents an appropriate approach to assessing ambulatory ability in boys with DBMD. A change in performance on the 6MWT constitutes a clinically meaningful endpoint and improvements would be a direct reflection of benefit to boys with DBMD. The 6MWT is feasible, accurate, and reproducible in the target population [McDonald 2010].

13.2.6.2 Timed Function Tests

These tests provide additional measures of ambulatory capability in boys with DMD who can still walk. Commonly employed over many years [Brooke 1989, McDonald 1995], these tests are relevant to the disease in that they assess functional aspects of proximal muscle strength required for everyday ambulation. Timed function tests are substantially abnormal in boys with DMD compared to healthy boys [Beenakker 2005b]. Worsening values have been correlated with time to wheelchair dependency [Brooke 1989, McDonald 1995]. These tests can be sensitive to medical intervention; corticosteroid therapy has documented improvements in all 3 parameters [Mendell 1989, Griggs 1991, Beenakker 2005a]. Given their long-standing use and simplicity, there is substantial experience with the conduct of the tests and the analyses of the data and very high reproducibility has been demonstrated [Mayhew 2007].

13.2.6.3 North Star Ambulatory Assessment

The NSAA is a functional scale specifically designed for ambulant DMD boys. The scale has been developed and piloted in the United Kingdom by the North Star Clinical Network for Paediatric Neuromuscular Disease Management with good intra and interobserver reliability and has recently been used in a large multicenter study [Mazzone 2011].

The scale includes items assessing abilities that are necessary to remain functionally ambulant, ie, ability to rise from the floor, ability to get from lying to sitting and sitting to standing, and that are known to progressively deteriorate in untreated DMD patients. The scale also includes items assessing head raise and standing on heels that can be partly present in the early stages of the disease and a number of activities such as hopping, jumping, and running [Mazzone 2010].

13.2.6.4 Egen Klassifikation

For nonambulatory patients with DMD, the EK scale has been selected to assess functional ability after loss of ambulation [Steffensen 2001]. The EK scale has previously been shown to be highly reliable when tested for intra- and inter-rater reliability among patients with DMD [Steffensen 2002a, Steffensen 2002b].

13.2.6.5 Spirometry

Progressive pulmonary dysfunction is a major source of disability and shortened survival associated with DMD and represents an important target for therapeutic intervention. Natural

history data in DMD show that pulmonary values decline more precipitously once patients lose ambulation [Steffensen 2002b].

Based on experience at measuring pulmonary function in randomized trials [Mendell 1989, Griggs 1991], it is clear that spirometry testing can be performed practically in multicenter studies enrolling study populations comparable to those to be enrolled into this study. Standard operating procedures for spirometry performance, requiring that spirometric effort is sufficient and that each test is consistent with American Thoracic Society/European Respiratory Society guidelines [Miller 2005a, Miller 2005b] will be used.

13.2.6.6 Disease Status Surveys

Information on patient and/or parent-reported changes in disease status (eg. disease symptoms and activities of daily living) during and after their participation in the prior PTC Therapeutics Studies 007 and 007e will be collected retrospectively through the use of a standardized survey administered by site personnel.

A separate survey will be administered by site personnel during the study to collect prospective information on patient and/or parent-reported changes in disease status.

14 BENEFITS AND RISKS

14.1 Benefits and Risks - Non-Clinical

Ataluren is an orally bioavailable small molecule intended for the treatment of nonsense Duchenne muscular dystrophy (nmDMD) resulting from a nonsense mutation in the dystrophin gene. In cellular assays and animal models of genetic disease, ataluren demonstrated the ability to specifically and selectively enable readthrough of mRNA containing a premature stop codon, inducing production of full-length protein that localizes to the appropriate cellular location and is functionally active. Ataluren consistently enabled mRNA readthrough and functional full-length protein production from mRNAs that contain a premature stop codon without promoting readthrough of normal stop codons.

Ataluren was shown to be selective for translation. Ataluren did not alter levels of mRNA with premature stop codons or wild type mRNA demonstrating that ataluren does not modify transcription or mRNA stability. In cell-free translation assays, ataluren functions at the level of translation and not transcription. Ataluren does not produce a functional protein by promoting readthrough of premature stop codons due to frameshift mutations (insertions or deletions) or of mRNAs harboring multiple sequential premature stop codons. Ataluren is selective for premature stop codons and does not promote readthrough of normal stop codons. In cellular models of nonsense mutation genetic diseases, ataluren exhibited a bell-shaped concentration response with maximal activity at 10 $\mu g/mL$. At ataluren concentrations above 20 $\mu g/mL$ a reduction in activity is observed, indicating a bell-shaped dose response. Cytotoxicity was not observed at any concentration tested. In animal models, ataluren exhibited a bell-shaped dose-response. In vitro and in vivo nonclinical efficacy pharmacology data indicate that concentrations that range from $\sim\!\!1$ to 20 $\mu g/mL$ were associated with pharmacodynamic activity.

Specifically, in the mdx mouse model, efficacy was associated with concentrations ranging from 2 to 10 µg/mL.

Toxicokinetic data were obtained in toxicity studies conducted in mice, rats, rabbits and dogs. Consistent with the short t¹/₂, there was no accumulation of drug in plasma upon repeated daily dosing. In all species, ataluren exposure increased with increasing dose, but the increase was generally less than dose proportional. There were no sex-related differences in ataluren exposure in dogs, but in rats and mice, exposure was slightly higher in females than in males. The major metabolite seen in mice, rats and dogs was ataluren acyl glucuronide; exposure to this metabolite in the toxicology species at LOAELs, NOAELs, and NELs in the toxicology program was greater than the exposure observed in humans administered the clinical dose of 10, 10 and 20 mg/kg/day at morning, midday, and evening, respectively. Ataluren is highly bound (> 97%) to plasma proteins in all species, including human. Ataluren is neither a substrate for nor an inhibitor of pglycoprotein. Enzyme inhibition studies with human liver microsomes showed that ataluren has a weak potential for direct inhibition of CYP2C8 and CYP2C9. As an added measure of safety, investigators should pay specific attention to use of drugs that are known substrates of these enzymes, particularly when such drugs may have a narrow therapeutic index. Enzyme induction evaluations in human hepatocytes showed that ataluren did not induce the activities of CYP450 enzymes. Induction of metabolism by ataluren is not expected since slight increases in CYP2B6 and CYP2C9 activity are observed only at an ataluren concentration that is 3- to 5-fold higher than the average peak concentration after a 20 mg/kg dose.

Based on in vitro studies, ataluren is a substrate of UGT1A9 and breast cancer resistant protein (BCRP). Caution should be exercised when ataluren is co-administered with drugs that are inducers of UGT1A9 (eg, phenobarbital, rifampin), or inhibitors of BCRP (eg, cyclosporine, eltrombopag, gefitinib).

In vitro data indicate that ataluren is an inhibitor of UGT1A9, organic anion transporter 1 (OAT1), organic anion transporter 3 (OAT3) and organic anion transporting polypeptide 1B3 (OATP1B3). Caution should be exercised when ataluren is co-administered with drugs that are substrates of UGT1A9 (eg, propofol, mycophenolate mofetil), OAT1, OAT3, or OATP1B3 (eg, oseltamivir, acyclovir, ciprofloxacin, captopril, furosemide, bumetanide, valsartan, pravastatin, rosuvastatin, atorvastatin, pitavastatin) because of the risk of increased concentration of these drugs.

Ataluren was evaluated in safety pharmacology studies and found to have no effects on the cardiovascular system, respiratory system, or central nervous system. In the toxicology program, the major findings observed were species-specific, ie, observed in one toxicology species only. These findings included kidney findings in mice (nephrosis, predominantly in the distal nephron, reversible following cessation of dosing) and adrenal gland cortical findings in dogs (lymphohistiocytic infiltrates with focal parenchymal cell degeneration in regions responsible for synthesis of glucocorticoids). Chronic studies were conducted in weanling rats and dogs to support dosing in children as young as 2 years of age. Ataluren was not genotoxic, and was not teratogenic in rats and rabbits. In rats and rabbits, fetal toxicity was observed only at maternotoxic doses. Ataluren had no effect on the fertility of male and female rats. In rats, postnatal developmental effects were observed only at materno-toxic doses. Maternal administration of

ataluren in rats had no effect on F₁ reproduction or F₂ embryo/fetal development. Ataluren did not increase the incidence of tumors in a 26-week carcinogenicity study in Tg.rasH2 mice. Tumors observed in rats in the toxicology program occurred at exposures that exceeded clinical exposure and were not considered relevant to humans. The structurally identified process impurities of the ataluren drug substance were qualified in rats at doses 29- to 33-fold higher than would be administered in the clinic at the proposed morning, midday, and evening doses of 10, 10 and 20 mg/kg/day, respectively. Ataluren is a small molecular weight compound, and therefore, is not expected to produce anti-drug antibodies. Ataluren had no effect on the immune system in the toxicology program and in the clinical trials; therefore, immunotoxicity studies were not performed with ataluren.

Nonclinical safety pharmacology and toxicology studies indicate that ataluren has an acceptable safety profile. The findings seen pose a low human safety risk and the program supports chronic administration of ataluren in patients as young as 2 years of age.

The nonclinical evaluation of ataluren presented in this summary support its use for the treatment of nmDMD.

